7.4 Reporting Procedures – Notifying the IRB

7.4.1 Adverse Event Reporting

The principal investigator will promptly notify the IRB of any unanticipated problems (UP) involving risks to subjects or others that occurs during the course of a study within **five working days** of learning about the event using Research Navigator.

7.4.2 Serious Adverse Event Reporting

Serious adverse events will be captured from the time of the main study's informed consent through 30 days after the last follow-up visit. The principal investigator will promptly notify the IRB of any unanticipated problems involving risks to subjects or others that occurs during the course of a study within **five working days** of learning about the event using Research Navigator.

According to 21 CFR 812.150(a)(1), the investigator will submit to the sponsor and to the reviewing IRB a report of any unanticipated adverse device effect occurring during an investigation as soon as possible, but in no event later than 10 working days after the investigator first learns of the effect. In addition, according to 21 CFR 812.150(b)(1), the sponsor who conducts an evaluation of an unanticipated adverse device effect under 812.46(b) will report the results of such evaluation to FDA and to all reviewing IRB's and participating investigators within 10 working days after the sponsor first receives notice of the effect. Thereafter the sponsor will submit such additional reports concerning the effect as FDA requests.

7.4.3 Unanticipated Problem Reporting

Incidents or events that meet the OHRP criteria for UPs require the creation and completion of an UP report form. It is the site investigator's responsibility to report UPs to their IRB. The UP report will include the following information:

- Protocol identifying information: protocol title and number, PI's name, and the IRB project number;
- A detailed description of the event, incident, experience, or outcome;
- An explanation of the basis for determining that the event, incident, experience, or outcome represents an UP;
- A description of any changes to the protocol or other corrective actions that have been taken or are proposed in response to the UP.

To satisfy the requirement for prompt reporting, UPs will be reported using the following timeline:

- **UPs that are SAEs** will be reported to the IRB within **5 working days** of the investigator becoming aware of the event.
- **Any other UP** will be reported to the IRB within **10 working days** of the investigator becoming aware of the problem.

7.4.4 Reporting of Pregnancy

If the subject participating in the study is found to be pregnant during the study period, participant will immediately be withdrawn from the study and IRB will be informed.

7.5 Reporting Procedures – Notifying the Study Sponsor

The study clinician will complete a SAE Form within the following timelines:

- All deaths and immediately life-threatening events, whether related or unrelated, will be recorded on the SAE Form and submitted to the study sponsor (PI) within 24 hours of awareness.
- Other SAEs regardless of relationship will be submitted to the study sponsor (PI) within 72 hours of site awareness.

All SAEs will be followed until satisfactory resolution or until the site investigator deems the event to be chronic or stable. Other supporting documentation of the event may be requested by the study sponsor and should be provided as soon as possible.

As a follow-up to the initial report, within the following 48 hours of awareness of the event, the investigator shall provide further information, as applicable, on the unanticipated event or the unanticipated problem in the form of a written narrative. This should include a copy of the completed Unanticipated Problem form, and any other diagnostic information that will assist the understanding of the event. Significant new information on ongoing unanticipated adverse effects shall be provided promptly to the study sponsor.

The study investigator shall complete an Unanticipated Adverse Device Effect Form and submit to the study sponsor and to the reviewing IRB as soon as possible, but in no event later than 10 working days after the investigator first learns of the effect. The study sponsor contact information is provided in Section 1, Key Roles.

As a follow-up to the initial report, within the following 48 hours of awareness of the event, the investigator shall provide further information, as applicable, on the unanticipated event or the unanticipated problem in the form of a written narrative. This should include a copy of the completed Unanticipated Problem form, and any other diagnostic information that will assist the understanding of the event. Significant new information on ongoing unanticipated adverse effects shall be provided promptly to the study sponsor.

The study sponsor is responsible for conducting an evaluation of an unanticipated adverse device effect and shall report the results of such evaluation to FDA and to all reviewing IRBs and participating investigators within 10 working days after the sponsor first receives notice of the effect. Thereafter the sponsor shall submit such additional reports concerning the effect as FDA requests.

7.6 Reporting Procedures – Notifying the FDA

The study sponsor (PI) is required to report certain study events in an expedited fashion to the FDA. These written notifications of adverse events are referred to as IND/IDE safety reports.

The following describes the IDE safety reporting requirements by timeline for reporting and associated type of event:

- **Within 10 working days** (via telephone or facsimile report)
Any study event that is:
 - associated with the use of the study device, and
 - unanticipated,
 - regardless of the seriousness of the event.
- **Within 5 working days** (via written report)
 - Protocol deviation to protect the life of the subject in emergency
 - Withdrawal of IRB approval
 - Lack of informed consent

Reporting Process

Adverse events may be submitted on FDA Form 3500A (MEDWATCH Form [available in study regulatory binders], or in a narrative format.

7.7 Study Halting Rules

Administration of study device will be halted when three severe AEs determined to be “probably related” or “related” to the study device are reported to the study sponsor. In such cases, enrollment screens will stop accepting new study participants until determination of safety is reviewed by the study sponsor. The study sponsor will inform the FDA of the temporary halt and the disposition of the study.

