7.2 Classification of an Adverse Event

7.2.1 Severity of Event

The Investigator will assess the severity (intensity) of each adverse event as mild, moderate, severe, life-threatening / disabling event, or death / unexpected pregnancy abortion. The investigator will also categorize each adverse event as to its potential relationship to study device.

The severity and causality of all adverse events will be graded according to the new adverse event classification by the Society of Interventional Radiology Standards of Practice Committee [62], as follows:

- **Mild AE:** No therapy or nominal (non-substantial) therapy (postprocedural imaging performed and fails to show manifestation of AE); near miss (e.g., wrong site of patient prepared, recognized and corrected before procedure, wrong patient information entered for procedure);
- **Moderate AE:** moderate escalation of care, requiring substantial treatment, e.g., intervention (description of intervention and result of intervention) under conscious sedation, blood product administration, extremely prolonged outpatient observation, or overnight admission after outpatient procedure not typical for the procedure (excludes admission or hospital days unrelated to AE);
- **Severe AE:** marked escalation of care, i.e., hospital admission or prolongation of existing hospital admission for > 24 hours, hospital admission that is atypical for the procedure, inpatient transfer from regular floor/telemetry to intensive care unit, or complex intervention performed requiring general anesthesia in previously non-intubated patient (generally excludes pediatrics or in circumstances in which

general anesthesia would primarily be used in lieu of conscious sedation, e.g., in mentally challenged or severely uncooperative patients);

- **Life-threatening or disabling event:** e.g., cardiopulmonary arrest, shock, organ failure, unanticipated dialysis, paralysis, loss of limb or organ;
- **Patient death or unexpected pregnancy abortion.**

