7.2.2 Relationship to Study Agent

For all collected AEs, the clinician who examines and evaluates the participant will determine the AE's causality based on temporal relationship and his/her clinical judgment. The degree of certainty about causality will be graded using the categories below according to the new adverse event classification by the Society of Interventional Radiology Standards of Practice Committee

- **Category 1:** AE not caused by procedure. The AE is completely independent of study drug administration, and/or evidence exists that the event is definitely related to another etiology. There must be an alternative, definitive etiology documented by the clinician.
- **Category 2:** Unknown whether AE was caused by the procedure.
- **Category 3:** AE caused by the procedure. There is clear evidence to suggest a causal relationship, and other possible contributing factors can be ruled out.

The definition implies a reasonable possibility of a causal relationship between the event and the study device. This means that there are facts (evidence) or arguments to suggest a causal relationship.

The following factors should also be considered:

- The temporal sequence from study procedure: The event should occur after the study procedure. The length of time from study procedure to event should be evaluated in the clinical context of the event.
- Underlying, concomitant, intercurrent diseases: Each report should be evaluated in the context of the natural history and course of the disease being treated and any other disease the patient may have.
- Concomitant procedures / treatments: The other drugs the patient is taking or the treatment the patient receives should be examined to determine whether any of them might be recognized to cause the event in question.
- Known response pattern for this class of study procedure: Clinical and/or nonclinical data may indicate whether a particular response is likely to be a class effect.
- Exposure to physical and/or mental stresses: The exposure to stress might induce adverse changes in the recipient and provide a logical and better explanation for the event.

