7.8 Safety Oversight

It is the responsibility of the sponsor/Principal Investigator (PI) to oversee the safety of the study. This safety monitoring will include careful assessment and appropriate reporting of adverse events as noted above, as well as the construction and implementation of a site data and safety-monitoring plan.

Medical monitoring will include a regular assessment of the number and type of serious adverse events. Data (demographics, eligibility criteria), screening methods, and adverse events also will be assessed by the PI who is a fellowship trained interventional radiologist and licensed physician monthly to ensure study safety, compliance, and integrity/accuracy of data in accordance with the data safety monitoring plan.

An sub-investigator with orthopedic surgery specialty will be consulted for safety and adverse event evaluation prior to final determination by the study PI.

Administration of study procedure will be halted when three severe AEs determined to be “probably related” or “related” to study device are reported to the sponsor (PI). The PI will notify the study investigators immediately when the third grade 3 event is reported, and enrollment screens will stop accepting new study participants. The study sponsor will convene a meeting with study investigators by teleconference or in writing as soon as possible and will provide recommendations for proceeding with the study. The study sponsor will inform the IRB and FDA of the temporary halt and the disposition of the study.

The outcomes of these reviews, when adverse events are captured will be communicated directly with the IRB. A summary of these reviews will be submitted to the IRB as part of an annual progress report at Continuing Review.

8 Clinical Monitoring

Clinical site monitoring is conducted to ensure that the rights and well-being of human subjects are protected, that the reported trial data are accurate, complete, and verifiable, and that the conduct of the trial is in compliance with the currently approved protocol/amendment(s), with GCP, and with applicable regulatory requirement(s).

Monitoring for this study will be performed by the study PI once every 3 months.

Monitoring activities include communication with the sub-investigators and study site staff; review of the study site's processes, procedures, and records; and verification of the accuracy of data.

9 Statistical Considerations

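### The only count-based halting rule (7.7, repeated in 7.8) counts severe events but not worse ones, and uses a causality level that the protocol's own scale lacks

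*Combined protocol and SAP*

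**What the plan says.** Section 7.7 states the trigger: "Administration of study device will be halted when three severe AEs determined to be" probably related or related to the study device. Enrollment then stops until the sponsor has reviewed safety. Section 7.8 says the same of the procedure, "Administration of study procedure will be halted when three severe AEs determined to be" probably related or related to the device, and then describes the trigger differently: "The PI will notify the study investigators immediately when the third grade 3 event is reported".

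The severity scale is in 7.2.1. Each event is assessed as "mild, moderate, severe, life-threatening / disabling event, or death / unexpected pregnancy abortion". Severe means "marked escalation of care, i.e., hospital admission or prolongation of existing hospital admission" and similar steps. Examples of the next level up are "cardiopulmonary arrest, shock, organ failure, unanticipated dialysis, paralysis, loss of limb or organ". The levels are named, not numbered.

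The causality scale is in 7.2.2 and has three categories. Category 1 is not caused by the procedure. Category 2 is "Unknown whether AE was caused by the procedure". Category 3 is caused by the procedure, on clear evidence and with other contributing factors ruled out. Section 7.2.1 separately asks the investigator to "categorize each adverse event as to its potential relationship to study device".

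**The concern.** A halting rule should not become less sensitive as events become more serious. This one names a single severity level and leaves the two above it unmentioned, and the *grade 3* label in 7.8 (presumably the third of the five levels) supports the narrow reading. It also depends on a causality judgment that the protocol's classification has no code for.

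The gap concerns events the protocol foresees. Section 1.4.1 lists limb-threatening ischemia from non-target embolization, and death; 6.8 plans rescue treatment for limb ischemia. Because these are described risks, the expedited routes for unanticipated events in 7.4 to 7.6 need not open for a single such event, unless its nature, severity or frequency is out of line with the description (7.2.3). The count in 7.7 is the only provision that pauses treatment without a further decision, so its wording matters most for these events.

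**Working it through.** The plan gives no event rate or halting probability for this rule, so there is no figure to reproduce. The check compares the rule with the two scales it relies on.

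**Severity.** Among device-related events, let *s* be the number graded severe and *h* the number graded life-threatening/disabling or death. The threshold of three is from 7.7 and the levels are from 7.2.1.

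- Literal rule: halt when *s* ≥ 3.
- Rule with *or worse*: halt when *s* + *h* ≥ 3.

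| Device-related events | Literal count | Halt? | Count with *or worse* | Halt? |
|---|---|---|---|---|
| 3 severe | 3 | yes | 3 + 0 = 3 | yes |
| 2 severe, 1 death or life-threatening | 2 | no | 2 + 1 = 3 | yes |
| 2 severe, 3 life-threatening | 2 | no | 2 + 3 = 5 | yes |

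The first row shows that the rule can be applied. The other rows show that *h* never enters the literal count, however large it becomes.

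Could the definition of severe absorb the higher levels? A life-threatening event will often involve admission or a longer stay, and so also fit the text for severe. But 7.2.1 offers the five levels as alternatives for each event, and nothing in 7.7 or 7.8 says that an event assigned to a higher level also counts as severe.

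**Causality.** Setting the words of 7.7 against the codes of 7.2.2:

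| Words in 7.7 | Code in 7.2.2 |
|---|---|
| related | Category 3 |
| probably related | none |

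Because Category 3 requires other factors to be ruled out, a probable but unproven event falls most naturally into Category 2, together with events whose cause is simply unknown. Take two severe Category 3 events and one severe Category 2 event. If the investigator thinks the third probable, 7.7 counts 2 + 1 = 3 and halts; if not, it counts 2 and does not. The recorded codes are the same in both cases. A later sentence in 7.2.2 speaks of a reasonable possibility of a causal relationship with the device. That might move some probable events into Category 3, but it conflicts with the ruled-out requirement and does not settle the matter.

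**Other provisions.** Deaths and immediately life-threatening events reach the sponsor, who is the PI, within 24 hours (7.5). The PI reviews adverse events monthly and consults an orthopedic sub-investigator, and review outcomes go to the IRB (7.8). The study may be suspended for unacceptable risk (4.8). None of these sets a count.

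**The case against.** The strongest reply is that no sensible sponsor would count a hospital admission and ignore a device-related death. The PI hears of such events within 24 hours, can suspend under 4.8 and decides the outcome of the halt anyway. A cluster of deaths or life-threatening events would probably exceed the rarity described in 1.4.1 and so open the expedited routes. The site data and safety-monitoring plan mentioned in 7.8 is not among the documents and may define the terms. All of this stands, and it limits the practical consequence. It does not correct the rule: a fixed count exists so that the pause does not depend on judgment at that moment, and as written the count gives the wrong answer.

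Three stronger readings are tempting but unsupported.

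- A reader might infer that the rule undercounts probably related events. It does not on its own words: 7.7 counts them expressly and nowhere limits the count to Category 3. What is missing is a recorded level that matches.
- A reader might infer, because the 7.2.2 categories refer to the procedure, that the count should take in procedure-only events such as access-site bleeding. Both sections tie the rule to the device, and 7.2.1 has device relationship assessed. Widening the rule would change its scope, which is a preference and not a correction.
- A reader might cite limb loss as an uncounted event that also escapes expedited reporting because it is a listed risk. Section 1.4.1 lists limb-threatening ischemia, not limb loss, so limb loss could qualify as unexpected in severity.

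**Conclusion.** The concern holds as a wording defect in a safety rule and should be corrected. Followed exactly, 7.7 and 7.8 do not halt for two severe events plus one death or life-threatening event, all device-related. They also rely on a probably related judgment that the 7.2.2 codes cannot show.

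The size is two omitted severity levels out of five and one causality level without a code. No probability of a missed halt can be given without assuming event rates that the documents do not supply. The severity conclusion rests on a literal reading, and on no unseen safety plan defining severe more broadly.

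The rule is neither absent nor unusable. The halt is temporary and is reviewed by the sponsor, who is the PI, so the gain from correcting it is a predictable pause and not an independent check. No efficacy result is affected.

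**What to change.** In 7.7 and 7.8, halt when three adverse events graded severe or worse under 7.2.1 (severe, life-threatening/disabling, or death) are judged related to the study device. Define related as Category 3, or Category 2 where the investigator records that a causal relationship is probable. In 7.8, replace *grade 3* with *severe or worse*. Keep the number three and keep the device as the referent.

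The cost is a wording amendment with IRB approval (12.2) and one yes/no item for each Category 2 event graded severe or worse. The downside is that a temporary halt may come somewhat sooner. Sample size and analyses do not change.

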7.8 Safety Oversight

It is the responsibility of the sponsor/Principal Investigator (PI) to oversee the safety of the study. This safety monitoring will include careful assessment and appropriate reporting of adverse events as noted above, as well as the construction and implementation of a site data and safety-monitoring plan.

Medical monitoring will include a regular assessment of the number and type of serious adverse events. Data (demographics, eligibility criteria), screening methods, and adverse events also will be assessed by the PI who is a fellowship trained interventional radiologist and licensed physician monthly to ensure study safety, compliance, and integrity/accuracy of data in accordance with the data safety monitoring plan.

An sub-investigator with orthopedic surgery specialty will be consulted for safety and adverse event evaluation prior to final determination by the study PI.

Administration of study procedure will be halted when three severe AEs determined to be “probably related” or “related” to study device are reported to the sponsor (PI). The PI will notify the study investigators immediately when the third grade 3 event is reported, and enrollment screens will stop accepting new study participants. The study sponsor will convene a meeting with study investigators by teleconference or in writing as soon as possible and will provide recommendations for proceeding with the study. The study sponsor will inform the IRB and FDA of the temporary halt and the disposition of the study.

The outcomes of these reviews, when adverse events are captured will be communicated directly with the IRB. A summary of these reviews will be submitted to the IRB as part of an annual progress report at Continuing Review.

8 Clinical Monitoring

Clinical site monitoring is conducted to ensure that the rights and well-being of human subjects are protected, that the reported trial data are accurate, complete, and verifiable, and that the conduct of the trial is in compliance with the currently approved protocol/amendment(s), with GCP, and with applicable regulatory requirement(s).

Monitoring for this study will be performed by the study PI once every 3 months.

Monitoring activities include communication with the sub-investigators and study site staff; review of the study site's processes, procedures, and records; and verification of the accuracy of data.

9 Statistical Considerations

9.1 Statistical and Analytical Plans (SAP)

A formal SAP will not be performed prior to database lock since this study is a pilot study with no randomization.

9.2 Statistical Hypotheses

This is a single arm study (i.e., no sham, placebo or alternative treatment included). The primary objective (clinical success rate) is a binary assessment of whether or not each patient achieved clinical success at 6 months post intervention.

The study is designed to test the null hypothesis (H_0) that the true proportion (PT) of patients that will manifest a positive treatment response, is no greater than 0.5 against the one-sided alternative hypothesis (H_A) that $PT \geq 0.75$.

The response rate will be summarized in terms of the observed proportion of patients manifesting a positive response and a two-sided exact 95% confidence interval (CI) per the Blyth-Still-Casella method (31). The treatment will be declared a success if the data support the conclusion that at least 75% of treated patients can be expected to show a positive response. The treatment will be considered unworthy of additional study without further

development if the data are consistent with the conclusion that no more than 50% of treated patients can be expected to show a positive response.

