Methodology	Prospective, single-arm (no sham or placebo), single-center
Endpoint	
Primary Efficacy endpoint: KOOS pain score at 6-months post intervention
 
Secondary endpoints:
 
 - Rate, type, causality, and severity of adverse events (AEs) - KOOS scores at 3-, 6-, 12-, and 24-month visits - QOL index value at 3-, 6-, 12-, and 24-month visits - Pain visual analog scale (VAS) at 3-, 6-, 12-, and 24-month visits - Magnetic Resonance Angiogram (MRA) findings at 6 and 24-month visits
Study Duration	4 years
Participant Duration	Each individual subject will be enrolled for approximately 25 months to complete all study visits from the initial screening visit to last follow up at 24-months post intervention
Population	40 patients, age 30-85, of any gender, with knee pain resistant to conservative management for at least 9 months post TKA.
Study Sites	NYU Langone Health Hospitals
Number of participants	Data from 40 patients who complete 6-month visit will be required The study would enroll 50 patients to account for an attrition rate of 20%
Description of Study Agent/Procedure	Embozene™ Color-Advanced Microspheres are spherical, tightly calibrated, biocompatible, non-resorbable, hydrogel microspheres coated with an inorganic perfluorinated polymer used for embolization.
Key Procedures	GAE; a transcatheter arterial embolization of one or more genicular artery(ies) using Embozene™ Color-Advanced Microspheres

Statistical Analysis	
The primary objective is to assess the clinical success rate, which will be summarized in terms of the observed proportion of patients manifesting a positive response and a two-sided exact 95% confidence interval (CI) per the Blyth-Still-Casella method. The treatment will be declared a success if the data support the conclusion that at least 75% of treated patients show a positive response.
 
Preliminary analysis will be performed after 25% (10 subjects) of study sample size complete the 6-month follow-up visit.

----------------------	---

Schematic of Study Design

1 Introduction, Background Information and Scientific Rationale

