9.3 Analysis Datasets

Participants who received study device and complete at least one follow-up visit (3-month visit) will be included in the study analysis.

Preliminary analysis will be performed after 25% (10 subjects) of study sample size complete the 6-month follow-up visit.

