9.4 Description of Statistical Methods

9.4.1 General Approach

This is a single arm study (i.e., no sham, placebo or alternative treatment included). The primary objective (clinical success rate) will be assessed as a binary outcome of whether or not each patient shows clinical success as defined above. The response rate will be summarized in terms of the observed proportion of patients manifesting a positive response and a two-sided exact 95% confidence interval (CI) per the Blyth-Still-Casella method. KOOS pain scores and pain VAS will be assessed as mean and standard deviation.

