9.5 Sample Size

The sample size is selected based on primary objective so that the study will have 80% power at the 5% significance level for testing the null hypothesis $H_0: PT \leq 0.5$ against the alternative hypothesis $H_A: PT \geq 0.75$, where PT is the true proportion of patients that will manifest a positive treatment response. As a result, the study should have 40 patients who completed the 6 months visit since this sample size will endow the test with 80.4% power at a realized significance level of 0.047 with 20% attrition, the study will need 50 subjects to reach the target sample size.

With 20% with 20% attrition, the study will need to enroll 50 patients. The PI and sub-investigators determined that increase in the sample size is necessary to evaluate the role of GAE as a disease-modifying treatment option for knee OA. Since this current study is the only active study in the U.S collecting samples for biomarker analysis and the need for a larger sample size to evaluate changes in biomarker levels, an increase in sample size is needed.

10 Source Documents and Access to Source Data/Documents

Source data is all information, original records of clinical findings, observations, or other activities in a clinical trial necessary for the reconstruction and evaluation of the trial. Source data are contained in source documents.

Examples of these original documents, and data records include: hospital records, clinical and office charts, laboratory notes, memoranda, subjects' diaries or evaluation checklists, pharmacy dispensing records, recorded data from automated instruments, copies or transcriptions certified after verification as being accurate and complete, microfiches, photographic negatives, microfilm or magnetic media, x-rays or other imaging studies, subject files, and records kept at the pharmacy, at the laboratories, and at medico-technical departments involved in the clinical trial. It is acceptable to use paper CRFs as source documents. Source CRFs can also be documented in the electronic medical record (EPIC).

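### The success rule (data supporting at least 75%) has no stated criterion and is not the hypothesis tested and powered, which is H0: PT ≤ 0.5

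*Combined protocol and SAP*

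**What the plan says.** Section 9.2 sets the null hypothesis that the true response proportion PT "is no greater than 0.5 against the one-sided alternative hypothesis" that PT is at least 0.75. Section 9.5 sizes the trial for that test at the 5% level and says of 40 six-month completers that "this sample size will endow the test with 80.4% power at a realized significance level of 0.047".

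The verdict is worded differently. In section 9.2: "The treatment will be declared a success if the data support the conclusion that at least 75% of treated patients" can be expected to respond. The Statistical Analysis row of the Protocol Summary repeats it: "The treatment will be declared a success if the data support the conclusion that at least 75% of treated patients show a positive response". A second sentence in 9.2 calls the treatment unworthy of further study if the data are consistent with a rate of 50% or less.

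Neither sentence comes with a cut-off. Section 9.4.1 says only that "The response rate will be summarized in terms of the observed proportion of patients manifesting a positive response" together with a two-sided exact 95% Blyth-Still-Casella interval. Section 9.4.2 names the endpoint and gives no decision rule. Section 9.1 adds: "A formal SAP will not be performed prior to database lock".

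**The concern.** The plan has a test without a verdict and a verdict without a test. The test is against 50%; the verdict is about 75%. Writing the alternative as PT ≥ 0.75 does not join them, because rates between 0.50 and 0.75 then belong to neither hypothesis, and rejecting PT ≤ 0.5 does not exclude them.

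If rejection of 50% is taken as success, the declared conclusion does not follow from it. If 75% itself has to be shown, that test is neither planned nor powered. If an observed rate of 75% is meant, no section says so. The trial is single-arm and open-label and will have no SAP before database lock, so the choice between these readings could be made with the results in view.

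**Working it through.** **Inputs.** p0 = 0.50 and p1 = 0.75 (section 9.2); one-sided 5% level, 40 six-month completers, and the stated pair of 80.4% power and alpha 0.047 (section 9.5); two-sided exact 95% interval (sections 9.2 and 9.4.1).

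**Formula.** With X the number of responders among n, P(X ≥ k | p) = Σ_{x=k..n} C(n,x) p^x (1−p)^(n−x). The cut-off for a one-sided level-α test is the smallest k with P(X ≥ k | p0) ≤ α.

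**The plan's own figure.** At n = 40:
- P(X ≥ 25 | 0.5) = 0.077, which is too large.
- P(X ≥ 26 | 0.5) = 0.040, so the cut-off is 26.
- P(X ≥ 26 | 0.75) = 0.946.

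The test therefore has alpha 0.040 and power 94.6%, not 0.047 and 80.4%. A search over n = 5 to 120 finds one match to the stated pair: n = 23 with at least 16 responders (alpha 0.0466, power 0.8037). The figures in 9.5 cannot be used to infer the intended cut-off at n = 40.

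**Readings of the success rule at n = 40.**

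| Reading | Responders needed | P(success) at PT = 0.60 | 0.65 | 0.70 | 0.75 |
|---|---|---|---|---|---|
| Reject PT ≤ 0.50, one-sided 5% | 26 (65.0%) | 31.7% | 57.2% | 80.7% | 94.6% |
| Observed rate at least 75% | 30 (75.0%) | 3.5% | 12.1% | 30.9% | 58.4% |
| Reject PT ≤ 0.75, one-sided 5% | 35 (87.5%) | <0.1% | 0.1% | 0.9% | 4.3% |
| 95% CI lower limit above 0.75 | 36 (90.0%) | <0.1% | <0.1% | 0.3% | 1.6% |

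The last two entries in the 0.75 column are small by construction, because 0.75 is the boundary being tested. At a true rate of 90% those two readings succeed with probability 79.4% and 62.9%.

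**Interval cut-offs.** Clopper-Pearson lower limits are 0.483 for 26/40, 0.509 for 27/40, 0.732 for 35/40 and 0.763 for 36/40. The shortest 95% acceptance regions at n = 40, which is the Blyth-Still-Casella logic, are 14 to 26 responders at p = 0.5 and 25 to 35 at p = 0.75. They give the same cut-offs of 27 and 36.

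**Collision at 26/40.** The one-sided test rejects 50% (p = 0.040). The Clopper-Pearson 95% interval is 48.3% to 79.4%, which contains both 50% and 75%. The same result rejects H0 and is still consistent with 50%, which is section 9.2's ground for calling the treatment unworthy.

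**The case against.** The best defence is that the test can be reconstructed. Section 9.2 gives a one-sided alternative, and section 9.5 gives a 5% level and speaks of a realized level, which makes sense only for an exact test with a critical count. At n = 40 that count is 26. Read this way, supporting 75% means rejecting H0 in favour of HA, and being consistent with 50% means not rejecting. The readings at 35 and 36 test a null of 0.75 that no section states, so the realistic dispute would be between 26 and 30 responders (94.6% against 58.4%). This is also a pilot, and the proportion and interval will be reported whatever the verdict.

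Part of this stands. The test of 50% can be made operational, and the 26-versus-30 contrast is the more realistic one. But the reconstruction confirms the second half of the problem: if rejecting 50% is success, the 75% conclusion is unsupported. The readings at 35 and 36 are what the success sentence literally says. Pilot status does not remove the issue, because section 9.2 commits to a two-way declaration.

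Two neighbouring matters do not decide this point. One is the mismatch of 80.4% and 0.047 with n = 40; section 9.5 mentions an increase in sample size for biomarker work, so the figures may have been carried over from a smaller design, but that is inference. The other is who is counted: section 9.3 says "Participants who received study device and complete at least one follow-up visit (3-month visit) will be included in the study analysis", whereas section 9.5 counts six-month completers.

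**Conclusion.** The point holds and should be fixed before any outcome analysis. The primary verdict has no stated criterion, and its wording claims more than the planned test can show. With 40 completers, results from 26 to 35 responders change verdict with the reading. Under the reading closest to the stated hypotheses, at least 75% would be claimed in 32%, 57% and 81% of trials at true rates of 60%, 65% and 70%.

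These figures assume exact binomial calculations, independent patients and 40 analysed. The interval cut-offs use Clopper-Pearson limits, checked against the shortest acceptance regions at n = 40 only.

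**What to change.** In section 9.2 and the Protocol Summary:

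- State HA as PT > 0.5, with 0.75 named as the design value for power.
- Declare success when H0: PT ≤ 0.5 is rejected by the one-sided 5% exact binomial test (at n = 40: at least 26, alpha 0.040, power 94.6%).
- Optionally, if the verdict should always agree with the reported two-sided 95% interval, require its lower limit to exceed 0.50 instead (at least 27 of 40, alpha 0.019, power 89.7%). This also removes the collision at 26/40.
- Define the rule by the test or the interval, not by a fixed count, because the number analysed may not be 40. The test cut-offs are 29 of 45 and 32 of 50; the interval cut-offs are 30 of 45 and 33 of 50 (Clopper-Pearson). A fixed count of 27 applied to 50 patients would have alpha 0.336.
- Replace the unworthy-of-study sentence with H0 not rejected.
- Drop at least 75% as the conclusion, or keep it only as a descriptive target for the point estimate.

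In section 9.5, restate alpha and power for the chosen rule.

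If the sponsor does want 75% as a bar for success, the plan must say so and state its operating characteristics. Requiring both rejection of 50% and an observed rate of at least 75% (30 of 40), for example, has 58.4% power at a true rate of 75%.

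The cost is wording in three places, submitted as an amendment for IRB approval (section 12.2). No patients are added, and power at 0.75 stays above 80% under either recommended rule. The downside is that a successful trial can claim only a response rate above 50%.
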